CBZ is absorbed slowly after oral administration with peak concentrations reached within 4-8 hours. This is mostly due to the time it takes for dissolution of CBZ tablets. The bioavailability is estimated at 75-85% and variably affected by food intake (19). CBZ is distributed throughout the body and ~75% is bound to albumin. It passes the blood-brain barrier, placenta and penetrates breast milk.

Safety

CBZ is a very safe drug with minimal side effects noted after extensive use (15). Side effects have led to reduction of dosage in only 3% of patients receiving the drug and to discontinuation of the drug in another 3%. Dose dependent side effects include drowsiness, sedation, vertigo and ophthalmoplegia. These tend to occur early in treatment and dissipate with chronic treatment in an overwhelming number of cases. Use of a dose escalation schedule also reduces the incidence of these side effects. Hyponatremia has been noted, especially in elderly patients. It is usually mild and asymptomatic. It may lower plasma concentrations of thyroid binding globulin, bound and unbound T4 and T3 but clinical hypothyroidism is rare. CBZ treatment may be associated with elevated serum transaminase levels in 5-10% of cases. In the vast majority of these cases CBZ can be continued without dose reduction. On rare occasions when evidence for hepatic dysfunction develops, CBZ must be discontinued.

Severe idiosyncratic reactions are rare. Hematological toxicity with aplastic anemia, agranulocytosis and or thrombocytopenia has been estimated to occur in less than 1 in 50,000 individuals treated with CBZ. A dose-dependent reduction in neutrophil count occurs in 10-20% of patients. However, the neutrophil count rarely goes below 1,200 per mm³ and CBZ administration has not been associated with an increase in infections. Allergic rash occurs in 4 to 10% of patients and is the most common reason for intolerance to CBZ. Allergic reactions with fever, renal and hepatic toxicity are very rare.

A Preliminary Study of the Efficacy and Safety of Carbamazepine in Severe Liver Disease Due to Alpha-1 Antitrypsin Deficiency

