3. Determine whether CBZ treatment reduces portal pressure in AT-deficient patients with severe liver disease as assessed by serial hepatic venous pressure gradient measurements
4. Determine whether CBZ treatment is safe and tolerated by patients with severe liver disease caused by AT deficiency
5. Determine whether CBZ treatment leads to stabilization in disease severity as measured by the MELD scores

STUDY DESIGN (See also Study Flow Chart in Attachment 2)

This is a Phase II prospective study of the use of CBZ in adolescents and adults with AT deficiency and compensated cirrhosis. It is a randomized, double-blinded, placebo-controlled study in which 20 subjects will receive drug and 10 subjects will receive placebo. Eligible patients will take CBZ or placebo for 12 months. Transvenous catheterization of the hepatic vein for measurement of hepatic venous pressure gradient will be carried out before and after the treatment period. Liver biopsies will be carried out through the transvenous catheterization at the same time to obtain liver tissue for measurement of hepatic ATZ load and hepatic fibrosis. These studies are often done as a part of standard of care for adults with cirrhosis. Clinical and biochemical follow-up will be undertaken to assess safety and tolerability of CBZ in these patients. After 12 months of therapy, HVPG and transvenous biopsies will be repeated permitting a formal assessment of effects on ATZ load (by PAS staining, immunostaining, and immunoblot analysis) and fibrosis (by quantitative Sirius red staining and by examination of changes in HVPG). This approach has been effectively utilized to demonstrate efficacy of antiviral therapy in both Hepatitis C and Hepatitis B in reducing portal pressure.

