The primary efficacy outcome will be to determine the effect of CBZ on hepatic ATZ load. This will be based on the number of hepatocytes with PAS+/diastase-resistant globules. Secondary measures will include the area of a liver section occupied by these globules. If there is enough tissue available for immunoblot analysis we will also use the steady state level of ATZ as a measure of hepatic ATZ load. For the secondary efficacy outcomes we will determine the effect of CBZ treatment on hepatic fibrosis on the basis of Sirius red staining and hydroxyproline concentration and whether CBZ treatment changes portal pressure as determined by HVPG. We will also determine if CBZ treatment reduces the MELD score by monitoring it at the beginning and end of the 12-month treatment period, including measuring at 7 follow-up visits while on active medication or placebo. The differences in the change in MELD score for subjects on active medication will be compared to that in subjects on placebo. Safety and tolerability will be investigated by close observation and routine laboratory testing of the 30 subjects.

A Preliminary Study of the Efficacy and Safety of Carbamazepine in Severe Liver Disease Due to Alpha-1 Antitrypsin Deficiency

STUDY POPULATION

Potential subjects for the study will be identified from the clinical practices of the pediatric and adult hepatology programs in the UPMC system and via outside referrals. The typical potentially eligible subject will have AT deficiency (ZZ and SZ phenotypes and low serum level) and clinical evidence of cirrhosis complicated by portal hypertension (e.g. splenomegaly or thrombocytopenia [platelet count <150,000 or a complication of portal hypertension (e.g. varices or ascites)]. HVPG measurement will be used as a screening procedure to determine if the potential study subject has documented significant portal hypertension (HVPG greater than or equal to 10 mm Hg or as indicated in inclusion criteria below). The research program will be advertised in relevant specialty journals and through the Alpha-1 Association. Interested individuals would need to be seen in the aforementioned clinical programs. Eligible subjects will be approached by one of the study investigators so that the study can be explained and inclusion/exclusion criteria can be reviewed.

SCREENING

Following a signed assent/consent, patients with AT deficiency will undergo a screening assessment to determine their eligibility for the interventional study.

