The only available data come from studies we have carried out in mice. We found statistically significant differences between 18 treated and 11 placebo mice in the number of globule-containing hepatocytes after CBZ treatment. At the end of the study there were an average of 1088 (sd=260) globule-containing hepatocytes among control and 323 (sd=179) globule-containing hepatocytes among treated mice (14). Assuming that the average number of globule-containing hepatocytes at baseline was the same in the two groups of mice, then the group difference at follow-up (765 globule-containing hepatocytes) reflects the group difference in changes. Assuming equal standard deviation (sd) in the two groups, the effect size was 3.5. Then, for the proposed sample size (20 treated:10 controls) and a two-sided type I error of 5% there would be 80% power even if the effect is 1.1, about 1/3 of what was found in mice. This translates to being able to detect a drop in the treated group of 765 globule-containing hepatocytes compared to a drop in the controls of 514 (rather than 0).

For the second objective of fibrosis the only relevant data come from hepatic hydroxyproline concentrations in mice after CBZ treatment. There were statistically significant differences between the treated and placebo groups in hepatic hydroxyproline concentrations after CBZ treatment with values of 2.27 (sd=1.02) in 24 control mice and 1.21 (sd=0.70) in 25 CBZ-treated mice (14). Assuming that the hepatic hydroxyproline concentrations at baseline were the same in the two groups of mice, then the group difference at follow-up (1.06) reflects the group difference in changes. Assuming equal standard deviation (sd) in the two groups, the effect size was 1.2. Then, for the proposed sample size (20 treated:10 controls) and a two-sided type I error of 5% there would be 80% power even if the effect is 1.1, about 1/10 of what was found in mice. This translates to being able to detect a drop in the treated group of 1.06 compared to a drop in the controls of 0.106 (rather than 0).

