For the third objective of portal pressure, power calculations utilized information from 3 studies in which statistically significant and clinically relevant changes in HVPG were demonstrated in small numbers of individuals treated with antiviral drugs. A drop of ~2 mm Hg, or 20%, was found in response to drug treatment (26-28). With 20 patients treated with drug and 10 treated with placebo, there would be 80% power, assuming an average drop in portal pressure of 3.4 or more mm Hg in the treated group compared with no change in the placebo group, with a standard deviation of 3 mm Hg for the measurements.

To increase recruitment, subjects in which an HPVG cannot be measured but have collateral intrahepatic vessels visualized via fluoroscopy, may be enrolled if they meet all other criteria. We expect the possibility of a loss of 20% of the patients for the primary aim due to no HVPG measurement. We expect the loss to be balanced in the intervention and placebo group. With 16 intervention/8 placebo as a sample size, we would have power to find an effect size of 1.2 demonstrating that we have adequate power.

A Preliminary Study of the Efficacy and Safety of Carbamazepine in Severe Liver Disease Due to Alpha-1 Antitrypsin Deficiency

Statistical Support, Data Management and Quality Control

The study administrator will prepare data collection forms and manuals of operations and will monitor study adherence to the trial protocol.

Safety analysis of this limited group of study subjects will be descriptive and will indicate tolerability of carbamazepine by individuals with compensated cirrhosis. Descriptive statistics of laboratory parameters at the end of therapy and at the time point of largest deviation from normal will be compiled.

The prevalence of other potential toxicities (e.g. dermatologic reactions) will also be compiled. Limited comparisons to the control group will be performed, although the study is not powered to identify relatively rare toxicities.

Approach to safety/tolerability

Clinical adverse events or laboratory value abnormalities requiring treatment reduction or discontinuation will be recorded. Particular attention will be placed upon potential serious adverse events known or believed to be related to CBZ that are fatal, potentially life threatening, significantly or permanently disabling, or require hospitalization.

Safety analysis

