A Preliminary Study of the Efficacy and Safety of Carbamazepine in Severe Liver Disease Due to Alpha-1 Antitrypsin Deficiency

4. Evidence of anticonvulsant hypersensitivity syndrome.
5. Leukocyte count <1,000 despite 2 weeks of CBZ dose reduction.
6. Neutrophil count <500 despite 2 weeks of CBZ dose reduction.
7. Platelet count <20,000 despite 2 weeks of CBZ dose reduction.
8. Hemoglobin <8.5 mg/dl.
9. INR greater than or equal to 2.5 not corrected by vitamin K 5 mg.
10. ALT >750 IU/L.
11. Pregnancy.
12. Breast feeding.
13. Evidence for behavior or ideation predisposing to suicide or increase in C-SSRS score of 1 from previous test score.
14. Persistent non-adherence to medication study regimen.

DATA RETRIEVAL AND STORAGE

A data repository in the University of Pittsburgh computing facility has been established to accept all information about subjects including; demographics, history, physical exam, labs and a tracking/event file. The tracking/event file is designed for important events: study entry; study completion; adverse events; treatment failures; exits; dropouts; protocol violations; etc. Security of the deposited data will be maintained through the use of unique patient identifier numbers and passwords to enter the repository. Data can be exported from the repository for reporting and statistical analysis.

Data quality and accuracy will be audited annually by comparing what is in the database with the medical records of the patients.

The electronic data storage and retrieval system used for the purpose of this clinical investigation has not been fully validated for compliance with the FDA regulations at 21 CFR Part 11 taking into account the limited size and scope of the investigation.

DATA AND SAFETY MONITORING PLAN

The Data and Safety Monitoring Board (DSMB) will consist of individuals who are independent of the institutions and investigators participating in the CBZ study, and who have no financial ties to the outcome of the trial. The ongoing review of the data by this independent committee assures the investigators and the study sponsor that the trial can continue without jeopardizing patient safety. Individuals on the DSMB will be responsible for monitoring data and safety during the course of this study.

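### The 80% power for globules and fibrosis assumes that all 30 subjects give paired biopsies; the plan should state this and show what assumed loss does, which matters mainly for fibrosis

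*Combined protocol and SAP*

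**What the plan says.** Under Study Design, "20 subjects will receive drug and 10 subjects will receive placebo". Under Statistical considerations, Objective 1 is tested by an unpaired t-test on the change from baseline to follow-up in globule-containing hepatocytes. Objective 2 uses the same method for hepatic hydroxyproline.

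Under Power calculations, both objectives carry the same sentence: "for the proposed sample size (20 treated:10 controls) and a two-sided type I error of 5% there would be 80% power" at an effect of 1.1. The plan sets this against mouse effects of 3.5 (globules) and 1.2 (hydroxyproline).

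One allowance for loss appears, under the third objective: "We expect the possibility of a loss of 20% of the patients". That sentence goes on to name the primary aim and to give absence of an HVPG measurement as the reason. The plan then reports a 16:8 case with an effect size of 1.2, without stating the power level.

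Elsewhere the plan lists 14 withdrawal criteria and keeps a tracking file that covers "adverse events; treatment failures; exits; dropouts; protocol violations". It also has the DSMB review attrition and retention. On-treatment assessments provides for liver tissue at transplantation, and at autopsy if the family consents.

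**The concern.** A change score needs two evaluable biopsies about a year apart. The power calculation uses the numbers randomised, so it treats all 30 pairs as certain in subjects with severe liver disease. The withdrawal criteria and the dropout tracking show that the plan allows for subjects leaving. No section says that a subject who withdraws still has the week-52 biopsy.

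Fibrosis is the sensitive case. The effect said to be detectable (1.1) lies only slightly below the mouse effect (1.2), so a modest loss of pairs can use up the difference. A null fibrosis result might then be taken as better supported than it is.

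**Working it through.** **Inputs.** From Power calculations: "a two-sided type I error of 5"%, 20 treated and 10 controls, effect 1.1. The mouse data there are a difference of 765 with SDs 260 and 179 (18 treated, 11 control), and a difference of 1.06 with SDs 1.02 and 0.70 (24 control, 25 treated). The test comes from the Objective 1 analysis text. Biopsy-loss rates of 10% and 20%, equal in both arms, are assumptions.

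**Formula.** Unpaired t-test with df = n1 + n2 − 2 and noncentrality = d × √(n1·n2/(n1+n2)). Power is the probability that the noncentral t exceeds the two-sided 5% critical value in absolute size.

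**1. Reproduce the plan's figure (20:10, d = 1.1).** √(200/30) = 2.582, so the noncentrality is 1.1 × 2.582 = 2.840. With df = 28 the critical value is 2.048. Power is 78.3%. By normal approximation, Φ(2.840 − 1.960) = 81.1%. The printed 80% lies between the two. The effect that gives exactly 80% is 1.12 by t-test and 1.09 by normal approximation.

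**2. Mouse effects.** Globules: pooled SD 212.6, so 765/212.6 = 3.60. With the simple average of the two variances it is 3.43. The plan prints 3.5. Hydroxyproline: pooled SD 0.871, so 1.06/0.871 = 1.22. The plan prints 1.2.

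**3. Repeat on paired biopsies.**

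| Pairs | Assumed loss | Noncentrality at 1.1 | Power at 1.1 | Effect detectable with 80% power | Power at 1.2 |
|---|---|---|---|---|---|
| 20:10 | 0% | 2.840 | 78.3% | 1.12 | 84.9% |
| 18:9 | 10% | 2.694 | 73.6% | 1.19 | 80.6% |
| 16:8 | 20% | 2.540 | 68.0% | 1.27 | 75.4% |

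By normal approximation, power at 1.1 is 81.1%, 76.9% and 71.9%, and power at 1.2 is 87.3%, 83.6% and 79.1%. With the unrounded hydroxyproline effect of 1.22, t-test power is 85.8%, 81.7% and 76.6%.

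**4. Against the mouse effects.** Globules: 1.12/3.5 = 32%, 1.19/3.5 = 34% and 1.27/3.5 = 36%. Power at 3.5 exceeds 99.9% in all three cases. Fibrosis: the margin below 1.2 is 1.2 − 1.12 = 0.08 with no loss, 1.2 − 1.19 = 0.01 at 10% loss, and 1.2 − 1.27 = −0.07 at 20% loss.

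**5. The plan's own drug-intolerance figures.** The Safety section gives 3% discontinuation and says "Allergic rash occurs in 4 to 10% of patients and is the most common reason for intolerance to CBZ". If 5% (19:10) or 10% (18:10) of the CBZ arm alone lost its pair, power at 1.1 would be 77.5% or 76.6%. That is a loss of about 1 to 2 points.

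**6. How likely is no loss?** If each subject independently had a 3% chance of lacking a pair, all 30 pairs would be obtained with probability 0.97^30 = 40%. At 10% it is 0.90^30 = 4%.

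**The case against.** **The arithmetic is sound.** A reader might infer that the 80% is a miscalculation. It is not: 78.3% and 81.1% bracket it, and the gap comes from rounding 1.12 to 1.1. This stands. The point concerns an unstated condition.

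**No loss rate is given.** A reader might infer that the plan itself predicts 10–20% missing biopsies. It does not. The rash and discontinuation figures concern the drug in general use, and stopping the drug is not the same as missing the biopsy. Carriers of the two HLA risk markers are excluded. The caveat "If there is enough tissue available for immunoblot analysis" applies to an additional measure and says nothing about globule counts on stained sections. A dropout field and DSMB review of attrition are routine. Transplant tissue, and autopsy tissue with consent, would recover some pairs. All of this stands, so the loss figures must be labelled as assumed.

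**The primary objective is barely touched.** A reader might infer that the globule analysis is left underpowered against the effect the plan cites. At 20% loss the detectable effect is still about a third of the mouse effect, as the plan says. Whether a mouse effect carries over to patients is a separate question.

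**Fibrosis at 10% loss.** A reader might infer that the claim already fails there. It does not: power at 1.2 is still 80.6%.

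**A 16:8 case is already printed.** It is, and its label mentions the primary aim. But its stated reason is missing HVPG. The Objective 3 analysis text keeps subjects with collateral vessels and a baseline HVPG below 10 in every other outcome, so that reason does not remove their biopsies. Nor does the printed case settle the matter if read as covering biopsies: an effect of 1.2 at 16:8 gives 75.4% by the planned t-test and 79.1% by normal approximation.

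**Resources fixed the sample size.** The plan says so and concedes that only large effects are detectable. That is a reason not to ask for more subjects. It does not remove the need to state what the power figure depends on.

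**Conclusion.** The concern holds in a limited form. The 80% power for Objectives 1 and 2 is correct only if all 30 randomised subjects give evaluable biopsies at both times. The plan neither states that condition nor allows for a missing week-52 biopsy.

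Under assumed equal loss in both arms, power at 1.1 falls from 78% to 74% at 10% loss and to 68% at 20%, a drop of about 5 and 10 points. For globules the practical effect is small. For fibrosis the margin below the mouse effect is about zero at 10% loss and gone at 20%.

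These figures rest on the planned unpaired t-test, on the plan's use of end-of-study mouse SDs for change scores in patients, and on loss rates that the documents do not supply.

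**What to change.** Keep enrolment at 30. Under Power calculations:

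- For Objectives 1 and 2, state that the 20:10 figure refers to subjects with paired evaluable biopsies.
- Add two scenarios labelled as assumed loss. With 18:9 pairs (10% loss), power at 1.1 is 74% and 80% power is reached at an effect of 1.19. With 16:8 pairs (20% loss), these are 68% and 1.27.
- For Objective 2, say that at 10% loss 80% power holds only for about the full mouse effect (81% at 1.2), and that at 20% loss it is not reached (75%).
- In the same edit, correct the description of 1.1 as about a tenth of the mouse hydroxyproline effect. Since 1.1/1.2 = 0.92, it is about a tenth below that effect.

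The cost is a change of wording. No subjects, procedures or analyses are added. The downside is that the stated power looks less favourable.

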Objective 1. Determine whether CBZ treatment reduces hepatic ATZ load in AT-deficient patients with severe liver disease.

The primary analysis will test for differences between the treated and placebo groups in the change from baseline to follow-up in the number of hepatocytes with PAS+/diastase-resistant globules using an unpaired t-test (or nonparametric equivalent if appropriate). Given the small sample size, we do not assume that randomization will balance treated and placebo groups at baseline with respect to outcome variables. Therefore, we will compare changes over the course of the treatment rather than differences at the end of the treatment. Secondary analyses will look at the area of a liver section occupied by these globules and the

A Preliminary Study of the Efficacy and Safety of Carbamazepine in Severe Liver Disease Due to Alpha-1 Antitrypsin Deficiency

steady state level of ATZ by immunoblot again using an unpaired t-test (or nonparametric equivalents if appropriate) of the differences between the treated and placebo groups in changes from baseline to follow-up.

Given that the sample is small, randomization may not balance the groups with respect to important covariates, though our ability to detect statistically significant differences is likewise limited to relatively large effect sizes. Furthermore, the number of variables that could be adjusted for in a regression model is also limited by the sample size, as is our ability to do subgroup analyses. However, as exploratory analyses, we will compare the distributions of important confounders between treated and placebo groups and fit multiple linear regression models that include independent variables, in addition to treatment group and baseline values of outcome measures, with variables whose distributions are markedly imbalanced between treatment groups.

Objective 2. Determine whether CBZ treatment reduces hepatic fibrosis in AT-deficient patients with severe liver disease.

Analysis will proceed as in objective 1; however, the outcome will be hepatic fibrosis. The primary analysis will compare treatment group differences in baseline to follow-up changes in hepatic hydroxyproline concentration using an unpaired t-test (or nonparametric equivalent if appropriate). Secondary outcome measures will include Sirius red staining of the liver. Exploratory analyses using multiple regression models will proceed as described above.

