Objective 3. Determine whether CBZ treatment reduces portal pressure in AT-deficient patients with severe liver disease as assessed by serial hepatic venous pressure gradient measurements.

Analysis will proceed as in objective 1; however, the outcome will be portal pressure. The analysis will compare treatment group differences in baseline to follow-up changes in hepatic wedge pressure gradient as the outcome. An unpaired t-test (or nonparametric equivalent if appropriate) will be the primary analysis and we will conduct exploratory multiple regression analyses to adjust for the possibility of covariate imbalances as described above.

In subjects with intrahepatic collateral vessels (visualized radiologically) together with HVPG less than 10 at baseline, we will assess the outcomes in all categories other than objective 3

It is possible that we will not see a difference in hepatic ATZ load or fibrosis because of variability and heterogeneity within the liver but that the drug will produce a stabilization or improvement in overall clinical status. Therefore, as an exploratory analysis we will assess whether CBZ treatment will lead to stabilization or improvement in disease severity as measured by the MELD score. The analysis will compare treatment group differences in baseline to follow-up changes.

Analysis will proceed as above; however, the outcome will be the MELD score. Unpaired t-tests (or nonparametric equivalent if appropriate) will be the primary analysis and we will conduct exploratory multiple regression analyses to adjust for the possibility of covariate imbalances.

A Preliminary Study of the Efficacy and Safety of Carbamazepine in Severe Liver Disease Due to Alpha-1 Antitrypsin Deficiency

Power calculations

Resources limited the sample size, so we performed power calculations with an effect size estimated from prior work on the primary outcome for this study – the number of hepatocytes with PAS+/diastase-resistant globules.

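### The fibrosis power statement puts the detectable effect at about one tenth of the mouse effect; by its own figures it is about nine tenths

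*Combined protocol and SAP*

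**What the plan says.** All the figures are in the combined protocol and SAP, under Statistical considerations.

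- **Power calculations, opening.** The sample size was not derived from a target effect: "Resources limited the sample size, so we performed power calculations with an effect size estimated from prior work on the primary outcome".
- **Power calculations, globules (Objective 1).** The mouse effect size is given as 3.5 and the detectable effect is described thus: "there would be 80% power even if the effect is 1.1, about 1/3 of what was found in mice".
- **Power calculations, fibrosis (Objective 2).** Hydroxyproline averaged 2.27 (SD 1.02) in 24 control mice and 1.21 (SD 0.70) in 25 treated mice, a difference of 1.06. Then: "Assuming equal standard deviation (sd) in the two groups, the effect size was 1.2". Then, for 20:10 and a two-sided 5% level: "there would be 80% power even if the effect is 1.1, about 1/10 of what was found in mice". The closing sentence puts this on the raw scale: "being able to detect a drop in the treated group of 1.06 compared to a drop in the controls of 0.106".
- **Analysis, Objective 2.** Hydroxyproline is the lead fibrosis measure: "The primary analysis will compare treatment group differences in baseline to follow-up changes in hepatic hydroxyproline concentration", by unpaired t-test or a nonparametric equivalent.

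**The concern.** The fraction conflicts with the numbers on both sides of it. An effect of 1.1 cannot be a tenth of an effect of 1.2.

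It matters because the fraction is the sentence's plain-language claim about robustness: how far the mouse effect could shrink in patients with power still at 80%. Since resources fixed the size of the trial, the job of this section is to tell readers what 30 subjects can detect. As printed, fibrosis has a tenfold margin, wider than the threefold margin claimed for the primary globule endpoint. The mouse effect sizes, 1.2 for fibrosis and 3.5 for globules, say the reverse. A reader who trusted the printed fraction could take a null fibrosis result as evidence against even a small benefit, when the trial has little power for anything much smaller than the mouse effect.

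**Working it through.** **Inputs** (Power calculations, fibrosis paragraph): 20 treated and 10 control subjects; two-sided α = 0.05; mouse SDs 1.02 (n = 24) and 0.70 (n = 25); mouse difference 1.06; stated mouse effect 1.2; stated detectable effect 1.1; raw translation 1.06 versus 0.106. Like the plan, I apply the mouse SDs to the change from baseline in patients.

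**1. Mouse effect size.**
- Simple average of variances: SD = √[(1.02² + 0.70²)/2] = 0.875, so d = 1.06/0.875 = 1.21.
- Weighted by degrees of freedom: SD = √[(23 × 1.02² + 24 × 0.70²)/47] = 0.871, so d = 1.06/0.871 = 1.22.

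The stated 1.2 is reproduced.

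**2. Power at d = 1.1.** The standard error factor is √(1/20 + 1/10) = 0.387, so the noncentrality is 1.1/0.387 = 2.84.
- Noncentral t, 28 df: 78.3%.
- Normal approximation: 81.1%.

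The stated 80% is reproduced to within 2 points. The effect giving exactly 80% is (1.960 + 0.842) × 0.387 = 1.085 by the normal approximation and 1.124 by noncentral t, so 1.1 is a fair rounding.

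**3. The fraction.**
- Stated effect sizes: 1.1/1.2 = 0.92.
- Raw scale: (1.06 − 0.106)/1.06 = 0.954/1.06 = 0.90.
- Exact 80% effects over the unrounded mouse effect: 0.89 (normal) to 0.93 (noncentral t), across both SD poolings.
- Stated: 0.10.

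The discrepancy is 0.90/0.10 = 9.0-fold on the raw scale and 0.917/0.10 = 9.2-fold on the effect-size scale. No choice of SD or method brings the fraction near 0.10.

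**4. Where the 1/10 comes from.** 0.106/1.06 = 0.10. That is the share of the mouse effect that may be lost, not the share that must remain.

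**5. How the same phrase is used for globules.** 1.1/3.5 = 0.31 and (765 − 514)/765 = 0.33. There, 'about 1/3' is the share that must remain. The same wording thus carries opposite meanings in two consecutive paragraphs.

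**6. Power if the mouse effect shrinks** (20:10, two-sided 5%, SD 0.875, noncentral t):

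| Share of mouse effect | d | Power |
|---|---|---|
| 1 | 1.212 | 86% |
| 9/10 | 1.091 | 78% |
| 3/4 | 0.909 | 62% |
| 1/2 | 0.606 | 33% |
| 1/10 | 0.121 | 6% |

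Using SD 0.871 moves each figure by 0.4 points or less.

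**The case against.** The best defence is that this is a one-word slip with the correct numbers beside it. The mouse effect of 1.2, the detectable effect of 1.1 and the raw translation are all right, and a reader who compares 1.1 with 1.2 sees the narrow margin at once. The authors may have meant one tenth *less than* the mouse effect, which would match the next sentence. Fibrosis is a secondary efficacy outcome under Study design, the Objective 1 analysis text warns that only relatively large effects are detectable, and no sample size, stopping rule or analysis uses the fraction.

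Most of this stands. A slip is the likeliest explanation, though that is an inference, and nothing in the design depends on it. But a slip that turns nine tenths into one tenth reverses the message of the sentence, and the globule paragraph leads the reader to take the fraction as a true ratio. The general caution about large effects does not correct a specific figure; it conflicts with a claimed tenfold margin. No other section corrects the fraction.

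A further point concerns the remedy: the plan gives no power curve for its other endpoints, and an added power figure from the t-test would sit beside an 80% that lies between the t and normal results. At half the mouse effect the two methods give 33% and 35%, so the gap is small, but the method should be named if the sentence is added.

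**Conclusion.** The concern holds. The detectable fibrosis effect is about nine tenths of the mouse effect (0.90 to 0.92 from the plan's figures, 0.89 to 0.93 recomputed), not one tenth. The stated margin is overstated about nine-fold: the trial tolerates a loss of roughly a tenth of the mouse effect, not nine tenths. Read literally, the text claims 80% power where there is about 6%.

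The ratio needs only the plan's own numbers. The power figures also rest on the plan's assumptions that the mouse SDs apply to change from baseline in patients, that the groups have a common SD, and that all 30 subjects contribute data. The error is confined to the fraction. It should be corrected because it sits inside a stated power claim for the lead analysis of Objective 2, but it is not a design fault.

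**What to change.** In the fibrosis paragraph of Power calculations, replace 'about 1/10 of' with 'about 9/10 of', and change 'even if' to 'if', since the margin is small. Leave the next sentence (1.06 versus 0.106) as it is; it is consistent with nine tenths.

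Preferably add one sentence: *By a two-sided t-test on the same assumptions, power falls to about 33% for half the mouse effect and about 6% for one tenth of it.* The correction is complete without this sentence, but it states what 30 subjects can show on fibrosis.

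The cost is one phrase and one optional sentence. Sample size, test and endpoints are unchanged; the stated margin becomes less favourable.
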